8.5 Study Duration

The overall study is expected to last around six months and each patient's participation is expected to last around 42 days. Each patient's involvement in the study will last approximately 3 to 5 hours per study visit with a total time commitment expected to be around 30 hours for each patient.

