9 STUDY PROCEDURES

9.1 Study Schedule of Events

Table 1 on the next page consists of the scheduled assessments for each study visit.

Table 1: Schedule of Events

Assessment	Visit 1	Wash-out period* (7 Days)	First Treatment 2 times a day for 2 weeks			Wash-out period* (7 Days)	Second Treatment 2 times a day for 2 weeks		
			Visit 2 (Day 1 + 2 Days)	Visit 3 (Day 7 ± 2 Days)	Visit 4 (Day 14 ± 2 Days)		Visit 5 (Day 22 + 2 Days)	Visit 6 (Day 28 ± 2 Days)	Visit 7 (Day 35 ± 2 Days)
Informed Consent	X								
Inclusion/Exclusion	X								
Demographics/Medical History	X								
VAS Measurements			X	X	X		X	X	X
Dry Mouth Relief Questionnaire			X	X	X		X	X	X
Oral Tissue Exam using theChallacombe Scale Score	X		X	X	X		X	X	X
Dry Mouth Inventory			X	X	X		X	X	X
Patient Diary			X	X	X		X	X	X
Intra-Oral Photo **			X	X	X		X	X	X
PPAQ1			X	X	X		X	X	X
PPAQ2			X	X	X		X	X	X
PPAQ3			X	X	X		X	X	X
PPAQ4				X	X			X	X
PPUQ					X				X
Concomitant medication	X		X	X	X		X	X	X
Adverse Events			X	X	X		X	X	X

* Patients must undergo a washout period of at least 7 days prior to using either treatment

**Patients that opt in/consent to having a picture of their mouth taken. Photo must be taken as a pre-use measurement.

For details of the Study Questionnaires, see **Appendix A, B, C, D and E**.

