9.2 Visit 1 (Screening Visit)

Patients interested in participating the study will be consented and enrolled at Visit 1. Patients will be consented prior to conducting any study assessments.

The following will be completed at Visit 1:

- Obtain Informed Consent from the patient
- Verify Inclusion criteria has been met and no Exclusion Criteria has been met
- Collect Demographics
- Collect Medical History
- Collect Concomitant Medications
- Conduct the Oral Tissue Exam using the Challacombe Scale Score
- Schedule patient for future study visits

To ensure an effective washout period, the study product will not be provided to the patient during Visit 1 to avoid the patient starting the treatment before obtaining baseline data at Visit 2 (Baseline Visit). **Patients should be reminded to not to use any oral rinse products during the washout period, as described in Section 9.9.**

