9.3 Visit 2 (Baseline Visit)

The second visit will be the Baseline Visit and should occur 1 (+2) days after screening visit and could last up to 4 hours as it will collect pre-use and post-use information at multiple timepoints (5 min, 30 min, 60 min, 120 min, and 240 min).

Before starting any treatment, the following pre-use measurements must be assessed by the Investigator or designated study staff:

- Visual Analogue Scale (VAS)
- Oral Tissue Exam using the Challacombe Scale Score
- Intra-Oral Photo

Before starting any treatment, the following pre-use measurement must be completed by the patient:

- Dry Mouth Inventory (DMI)

Patients will not be allowed to eat or drink during the study visit except for when directed by study staff.

Once the VAS, DMI, the Oral Tissue Exam and Intra-Oral photo have been completed, the sealed envelope will be opened, and treatment order noted. The patient will then self-administer the first dose of the treatment into their mouth using the first sample assigned based on the randomization card.

The **post-use measurements** will include the following at the appropriate timepoints:

- 5 (+ 5) minutes after 1st dose: PPAQ1 (Questions 1-3; completed while patient is in clinic)
- 30 (± 10) minutes after 1st dose: PPAQ2 (Questions 1-11; completed while patient is in clinic)
- 60 (± 10) minutes after 1st dose: PPAQ3 (Questions 12-14; completed while patient is in clinic)
- 120 (± 10) minutes after 1st dose: VAS, Dry Mouth Relief Questionnaire (DMRQ), and PPAQ3 (Questions 12-14; completed while patient is in clinic)
- 240 (± 10) minutes after 1st dose: PPAQ3 (Questions 12-14; completed while patient is in clinic or completed at home)

Other Assessments/Schedule of Events that must be completed during Visit 2 include:

- Provide the patient with a patient diary and instructions as indicated below
- Review any changes in concomitant medications
- Review any side effects/adverse events
- Provide the patient with instructions to use the product at home
- Schedule the next follow-up visit (Visit 3) and instruct patients NOT to take the product the morning of Visit 3

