9.9 Washout Period

Patients will be required to undergo a washout period twice during the study. The first washout period should occur after the subject signs consent and will last until the baseline visit (Visit 2). The second washout period will start after the end of Visit 4 and last until the beginning of Visit 5. A washout period is necessary to ensure patients proceed to a new treatment period without carrying over any residual effects from previous treatment. During the washout period patients will be instructed *not* to use any over the counter or prescription products for dry mouth. Patients will be allowed to only use water to rinse their mouth during the washout period. If a patient uses any type of oral rinse to treat dry mouth during the washout period it will be considered a protocol deviation.

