3.1 Randomization

Patients will be randomized at Visit 1, after they have signed the consent form and have been confirmed that they had fulfilled the criteria for study inclusion and exclusion. A unique investigational number will be assigned to each patient as the study identifier after they have entered the study.

Patients who leave the study between signing the consent form and randomization will be replaced. But patients who leave the study after randomization are considered to be lost to follow-up and will not be replaced.

Each patient will be allocated with equal probability within blocks of six patients to one of:

- Group A: to receive MucoPEG in Period 1 and Biotène in Period 2

Statistical Analysis Plan		Page 11 of 17
Sponsor SunBio Inc.	Study Clinical Evaluation of MucoPEG for Xerostomia	Version 1.1

- Group B: to receive Biotène in Period 1 and MucoPEG in Period 2

Each period will last two weeks. There will be a washout period of one week between Visit 1 and Period 1 and between Period 1 and Period 2, during which patients will only use plain water as mouth rinse.

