3.3 Study Assessments

Patients are considered to be enrolled in this study after placing their signature on the consent form at Visit 1. Their eligibility to proceed and their concomitant medications will then be checked. Before Period 1 (the first use of MucoPEG or Biotène), patients will undergo one week of “washout” period.

During Period 1, which will last for two weeks, patients will use one of the products twice daily and will be assessed on the first day (Visit 2), seventh day (Visit 3) and fourteenth day (Visit 4) using the VAS, DMRQ, DMI, PPAQ, PPUQ. Information from symptom diary, medications, clinical examination and adverse events will also be recorded.

Another washout period of one week follows Period 1. The assessments for the second treatment will have the same pattern, with Visit 5, 6 and 7 to take place within Period 2.

4 Sample Size Determination

The hypotheses for this study are

- Null hypothesis
Change in VAS after MucoPEG minus change in VAS after Biotène ≥ 0
- Alternative hypothesis
Change in VAS after MucoPEG minus change in VAS after Biotène < 0

The change in VAS associated with each product will be calculated as the value of VAS at two hours after the final dose at Visit 4 minus the value of VAS before the first dose at Visit 2 for the first treatment period. Since the Visual Analogue Scale is constructed such that 0 = no symptom and 10 = most severe symptom, an improvement in symptom is represented by a negative change in its measurement. The hypotheses are to test whether patients would experience greater improvement in their symptoms after a course of MucoPEG.

Statistical Analysis Plan		Page 12 of 17
Sponsor SunBio Inc.	Study Clinical Evaluation of MucoPEG for Xerostomia	Version 1.1

The change in VAS for the second treatment period will be calculated in a similar way from the value of VAS before the first dose at Visit 5 and the value of VAS at two hours after the final dose at Visit 7.

Assuming the average difference between randomization groups is -1.25, a common standard deviation of 1.50 and a Type I error of 0.05 (one-sided probability), an effective sample size of 38 patients will provide 80% power to reject the null hypothesis of no difference between the two products (MucoPEG versus Biotène).

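### Protocol 9.3 places the baseline visit 1 to 3 days after screening, which cannot be reconciled with the 7-day first washout required by Table 1 and the SAP

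*Protocol*

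**What the plan says.** Protocol 9.3 gives the timing of Visit 2: "The second visit will be the Baseline Visit and should occur 1 (+2) days after screening visit". At that visit the patient completes the pre-use measures, including the VAS, and then takes the first dose of the assigned product.

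Other parts of the plan fix the length of the washout before that dose:

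- Protocol 9.1, footnote to Table 1: "Patients must undergo a washout period of at least 7 days prior to using either treatment". Table 1 also shows a separate 7-day washout column between Visit 1 and Visit 2, and labels the visit "Visit 2 (Day 1 + 2 Days").
- Protocol 9.9: "The first washout period should occur after the subject signs consent and will last until the baseline visit (Visit 2"). It gives the start and end but no length. Consent is taken at Visit 1 (Protocol 9.2).
- Protocol 9.2: "To ensure an effective washout period, the study product will not be provided to the patient during Visit 1".
- SAP 3.1: "There will be a washout period of one week between Visit 1 and Period 1 and between Period 1 and Period 2".
- SAP 3.3 repeats that, before Period 1, "patients will undergo one week of" washout.
- Protocol 8.5: each patient's "participation is expected to last around 42 days".

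**The concern.** The visit section is the text a coordinator uses to book appointments, and 9.2 has staff schedule the later visits at Visit 1. A coordinator who books Visit 2 from 9.3 breaches the Table 1 footnote; one who books it from the footnote falls outside the 9.3 window.

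The visit matters because its pre-dose VAS is the Period 1 starting value for the primary endpoint (SAP 2.3). No eligibility criterion bars over-the-counter dry-mouth products in the days before screening. Exclusion 8 concerns only unstable doses of systemic parasympathetic drugs. The washout that starts at consent is therefore the only product-free run-in of more than a few hours that the plan provides.

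Reporting is also at stake. A site that obeyed 9.3 had little reason to record a short washout as a deviation, and no planned table or listing specifies the interval from Visit 1 to Visit 2.

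**Working it through.** This is date arithmetic on the stated visit timings; sample size and error rates play no part.

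**Inputs**

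- Gap from Visit 1 to Visit 2 under Protocol 9.3: 1 day, plus up to 2, so 1, 2 or 3 days.
- Minimum washout before either product: 7 days (Table 1 footnote); one week (SAP 3.1, 3.3).
- Washout runs from consent at Visit 1 to Visit 2 (Protocol 9.2, 9.9), so its length equals the gap.
- Visit 7: nominally 35 days after baseline (Protocol 9.8).
- Stated participation: around 42 days (Protocol 8.5).

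**Step 1: reproduce the plan's own duration.** Participation = gap + 35.

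| Rule for Visit 2 | Gap (days) | Nominal participation (days) |
|---|---|---|
| Table 1 footnote, at its minimum | 7 | 7 + 35 = 42 |
| Protocol 9.3, earliest | 1 | 1 + 35 = 36 |
| Protocol 9.3, latest | 3 | 3 + 35 = 38 |

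The stated figure is reproduced with a 7-day gap and not with the 9.3 gap. If Visit 2 is itself counted as Day 1, Visit 7 falls 34 days later. The results are then 7 + 34 = 41, against 1 + 34 = 35 to 3 + 34 = 37. The protocol says only that participation is around 42 days, so this is supporting evidence of intent; on either count the 7-day gap fits better.

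**Step 2: compare the two rules.** The 9.3 window contains 1, 2 and 3 days, none of which reaches 7. The shortfall is 7 − 3 = 4 to 7 − 1 = 6 days.

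**Step 3: look for a reading that reconciles them.** Abstinence before screening cannot count, because 9.9 starts the washout after consent and SAP 3.1 places the week between Visit 1 and Period 1. The +2 allowance is already in the 1-to-3-day range. The likely origin of the conflict is Table 1's label for Visit 2. There, Day 1 is the first treatment day, after the washout column; 9.3 appears to have carried the same figures over as days after screening.

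**Step 4: see what the planned outputs would show.** SAP 5.1.2 defines Study Day as 1 + assessment date − first dose date. Applied to Visit 1, this gives 1 − 1 = 0 to 1 − 3 = −2 under 9.3, and 1 − 7 = −6 or earlier under the footnote. The variable can therefore separate the two rules, but no output of it for Visit 1 is specified. SAP 5.1.3 analyses data by nominal visit even when out of window. SAP 5.11 summarises deviations reported on the CRF, and the listings in SAP 7 cover deviations and side effects or adverse events.

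**The case against.** The best reply is that this is a wording slip which the rest of the plan resolves. Section 9.3 uses advisory language where the footnote is mandatory. The 7-day column, SAP 3.1 and 3.3 and the 42-day duration all point the same way. That stands as evidence of intent: seven days is the rule the plan meant. It does not remove the conflict, since 9.3 is current text and is the section that tells sites when to hold the visit.

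A reader might go further and infer that the Period 1 baseline was contaminated, or that the product comparison is biased. The documents do not support either. No trial product precedes Visit 2, so carryover between the study products cannot arise in the first washout; only products used before the study could matter. The only relief duration given is up to 4 hours, for the comparator (Protocol 5.4), and even one day exceeds that. Inclusion criteria 6 and 8 add some protection: no oral care products for 2 hours before visits, and only supplied products during the study. Both sequence groups follow the same rule, and SAP 5.6.1 compares the products within each period.

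A reader might also infer that sites did give short washouts, or that the SAP could not reveal them. Nothing in the documents shows which rule was followed, and the Study Day formula would reveal it if it were tabulated for Visit 1.

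**Conclusion.** The inconsistency is real and wrong as written. Protocol 9.3 permits a first washout of 1 to 3 days where Table 1 requires at least 7 and the SAP states one week, a shortfall of 4 to 6 days, and no Visit 2 date meets both. This rests only on the quoted timings and on 9.9 starting the washout at consent.

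The consequence is limited. Seven days was evidently intended, no between-product bias is shown, and the size of any effect on VAS cannot be derived from the documents. What remains is a contradictory instruction for the baseline visit of the primary endpoint, together with a reporting plan that specifies no output showing which rule was followed. It should be corrected and documented, but it is not a reason by itself to doubt the product comparison.

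**What to change.** Change Protocol 9.3 so that Visit 2 falls at least 7 days after screening, for example 7 (+2) days. That gives a washout of 7 to 9 days and nominal participation of 7 + 35 = 42 to 9 + 35 = 44 days, in line with Table 1 and the stated duration.

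The SAP version history shows that the database is already locked, so the text change alone does not help this trial. In addition:

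- Derive the Visit 1-to-2 and Visit 4-to-5 intervals from recorded visit dates and report them by sequence group.
- Count every interval under 7 days as a deviation from the Table 1 footnote in the SAP 5.11 summary, whether or not the site recorded it.
- Decide any per-protocol exclusion by the criterion in Protocol 15.4, namely whether the deviation could affect measurement of the primary endpoint. SAP 5.2 refers only to major deviations. Label the decision post hoc, and note that it could remove most patients if sites followed 9.3.

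The cost is one corrected sentence, two derived intervals and one table. No new data should be needed: SAP 5.3 already relies on the Visit 1 date and SAP 5.1.2 on assessment dates. If every interval is at least 7 days, the table closes the question.

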9.9 Washout Period

Patients will be required to undergo a washout period twice during the study. The first washout period should occur after the subject signs consent and will last until the baseline visit (Visit 2). The second washout period will start after the end of Visit 4 and last until the beginning of Visit 5. A washout period is necessary to ensure patients proceed to a new treatment period without carrying over any residual effects from previous treatment. During the washout period patients will be instructed *not* to use any over the counter or prescription products for dry mouth. Patients will be allowed to only use water to rinse their mouth during the washout period. If a patient uses any type of oral rinse to treat dry mouth during the washout period it will be considered a protocol deviation.

9.10 Patient Diary

Patients will be given a patient diary at Visit 2 and instructed to record storage location of the product (i.e. was the MucoPEG™ stored in the freezer as indicated and was the Biotene® stored at room temperature, as indicated), the hours of use, and any side effects and/or adverse events they experience while using their assigned study product. Patients will also be asked an open question about how their mouth feels after using the product.

9.11 Intra-Oral Photograph

An intra-oral photograph of the mouth will be taken if patients have consented to have their photo taken. The intra-oral photo must be taken prior to administering any study product to the

patient. A total of 5 pictures should be taken as follows: 1) upper side – hard plate 2) tongue 3) buccal mucosa: right side 4) buccal mucosa: left side 5) floor of mouth. Intra-oral photographs will be taken at the designated visits as described in **Table 1**.

9.12 Concomitant Medications

Concomitant medications are prescription medications, over-the-counter (OTC) drugs or dietary supplements taken by a patient. Concomitant medications should be collected at Visit 1 and should include any medications that, in the opinion of the Investigator, could contribute to dry mouth.

10 TRAINING, STORAGE AND ACCOUNTABILITY

10.1 Training Requirements

Prior to investigation site activation or subsequent involvement in clinical study activities, the Sponsor or designated CRO will provide clinical study training relevant and pertinent to the involvement of personnel conducting clinical study activities.

10.2 Clinical Study Materials and Clinical Study-Specific Equipment

The sponsor or designated CRO will provide study documentation (e.g. Investigator Site File, eCRF access, Study Worksheets, etc.) and study devices to the site personnel.

The site personnel are responsible to send an acknowledgment of receipt to the sponsor or designee after receiving the study devices (via email or fax).

Where applicable, computer and internet access may be a pre-requisite for site participation.

10.3 Study Device/Product Traceability

10.3.1 Supply of Devices/Products

The study sponsor will have the product shipped directly to the investigational site.

10.3.2 Device Storage and Accountability

Full tracking must be performed as soon as the device/product is received by the investigator/investigation site. Devices/products received by the Site will be confirmed on the shipping documents. The MucoPEG™ provided by the Sponsor will be traced during the clinical study by assigning specific lot numbers, batch numbers, or serial numbers to each device/product.

All information for the use, storage and handling of the investigational device/product as indicated in the Instructions for Use must be taken into account.

10.3.3 Device/Product Return Procedures

The vendor of products manufactured by SunBio Inc., will collect the returned and any malfunction device/product.

11 PATIENT ACCOUNTABILITY AND WITHDRAWAL

11.1 Patient Withdrawals and Discontinuation

During this study, patients may choose to discontinue / leave the study for any of the following reasons:

- Patient's withdrawal of consent.
- Any unexpected adverse effect which, in the opinion of the Principal Investigator, is related to the device and will endanger the well being of the patient if the treatment is continued.
- The deterioration of any underlying illness(es), infection or condition(s) that might interfere with the Clinical Investigation Plan.
- Any problem deemed by the Principal Investigator and/ SunBio, Inc. to be sufficient to cause discontinuation.

Patients who are withdrawn from the study because of an unexpected adverse event will be treated until its resolution. The Principal Investigator will clearly document the date and reason(s) for patient withdrawal in his/her eCase Report Form (eCRF) or EDC system and the monitor must be notified.

Patients have the right to withdraw from the study at any time and for any reason without prejudice to their future medical care. If a patient decides to withdraw, all study tests and procedures will be stopped and the cause of withdrawal will be documented. The investigative site must account for and document all patients enrolled in the study, including those withdrawn from the study or lost to follow-up. If a patient withdraws from the clinical investigation, the reason(s) shall be reported on the eCRF.

Additional study data may no longer be collected after a patient's withdrawal. Data collected up to the point of withdrawal will be used for analysis. Patients who are withdrawn will not be replaced if they have received any of MucoPEG™ or Biotène® Dry Mouth Gentle Oral Rinse doses. Patients will be replaced if they are withdrawn prior to receiving the first dose on Visit 2.

11.2 Loss to Follow-Up

The minimum effort to obtain follow-up information includes 3 attempts to contact the patient (or their legally authorized representative) by telephone, and if not successful, a certified letter sent to the patient's last known address. All contact efforts to obtain follow-up information must be documented in both the patient's medical records and on the eCRFs.

12 SAFETY CONSIDERATIONS

12.1 Investigator Responsibilities

The Investigator is responsible for identifying adverse events throughout the study and follow-up period. An adverse event can occur at any time during the conduct of the study, in any phase of the study or after the study is completed. An adverse event can be identified by the Investigator or reported by the patient.

Note: The Federal Privacy Rule (HIPAA) specifically permits the use and disclosure of protected health information "without written authorization of the individual" when used for public health

activities such as reporting adverse events, tracking FDA-related products, enabling recalls, repairs, replacements, lookbacks, or conducting post-market surveillance [45 CFR 164.512]. This use and disclosure is patient to the *minimum necessary* standard, i.e. “the minimum necessary to accomplish the intended use, disclosure, or request” [45 CFR 164.502].

